8.4 Procedures

i) Recruitment

Potential subjects will be identified from the selected customer base of Össur. Customer representative evaluates, based on previous experience of interaction with and servicing of patients, if a potential participant is cognitively capable. The customer representative informs the PI / LPI of the potential subject and hands over their contact information. If a potential participant fits the inclusion and exclusion criteria the LPI will contact them via telephone. During the telephone call the LPI will verify if they are interested in participating in a study. If interest is expressed at that point they will answer some screening questions and if the eligibility criteria are met an appointment will be made for the clinical visit and signing of the ICF. Questions relating to the duration of the study, number of clinical visits required, and the investigational device will be answered.

Potential risk of participating in the investigation will be explained to the subject at this point to the candidate for enrolment.

The LPI will communicate to the study monitor the number of users he has identified that meet the inclusion criteria and are willing to participate.

ii) Test procedure

There are two scheduled study events. Up to 13 users will be recruited, 1 study site. At the initial visit, the first study event, for each subject a researcher qualified to obtain informed consent will seat the subject and proceed as described in chapter 13.8 Informed consent.

Prior to fitting the subject will be asked to provide feedback on the current prosthesis, by filling in a set of questionnaires (including subset of PEQ) and perform tasks of daily living like e.g., walking up/down ramps and stairs, level ground walking in different speeds and walking on uneven terrain.

The users will be fitted within the standard methods of prosthetic fitting and alignment will be documented.

After initial fitting of the investigational device, the subjects will receive standard training on the investigational device. The required training steps and exercises as well as the performance of the subject will be observed. Comments and initial feedback from the subject will be documented. When the training is completed, and subjects feel comfortable and safe they will take a short break. Afterwards they will be asked to perform the same tasks as with their prescribed prosthesis before.

A standardized set of questions regarding the performance of the investigational device and the subject's satisfaction will be asked as a semi-structured interview, and the responses are documented.

The activities are video recorded to visually compare the performance of the two devices.

If the user feels comfortable and safe, he will be asked to use the investigational device for 4 weeks. They will be asked to fill in a log file for e.g. use in water, use of the app, use of the locking function.

The LPI will contact the user after 2 weeks to check on any issues that may arise. The user has the option to stop the trial at any time, an appointment will be made to switch to the prescribed knee.

The second visit will be at 4 weeks after visit 1. During this visit subjects will complete the same functional tests and questionnaires as at visit 1 (excluding background information) on the investigational device. They will then be fitted back to their prescribed device and feedback will be collected.

iii) Measurements and data collection

The same questionnaires, consisting of one valid instrument (subset of PEQ questions) and device and performance specific questionnaires, will be used and filled in at two separate points in time. Background information will be collected at baseline only. An activity report will be generated from the investigational device at visit 2.

Table 7 Visit schedule and procedures

	Recruitment phase: 2-4 weeks prior to baseline	Subject visit 1: baseline	Subject visit 2: 4 weeks after visit 1
Potential subjects identified, fitting inclusion/exclusion criteria, by LPI from Össur customers		X	
LPI calls potential subjects and screens by telephone (Pain Scale, SFCS)		X	
Subject signs ICF		X	
Subject answers subset of PEQ		X	
Subject performs TUG, 2MWT and activities of daily living (Ramps, stairs, uneven terrain)		X	
Subject fills in set of questionnaires (ABC, PlusM)		X	
Subject fitted with investigational device and receives training according to training protocol		X	
Subject performs activities of daily living (Ramps, stairs, uneven terrain)		X	
Subject fills in set of questionnaires (Specific questions, comparison)		X	
Subject answers subset of PEQ		X	
Subject performs TUG, 2MWT and activities of daily living (Ramps, stairs, uneven terrain)		X	
Subject fills in set of questionnaires (ABC, PlusM)		X	
LPI prints out activity report from the investigational device/ prescribed device			X
Subject is fitted back to their prescribed prosthesis			X
Adhoc feedback			X
Subject performs activities of daily living (Ramps, stairs, uneven terrain)			X
Subject fills in set of questionnaires (Specific questions, comparison)			X
End of study			X

For each subject there are 2 scheduled visits to the study site and questionnaires/tasks/measurements administrated two times during the course of the study.

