	Hypothesis	Construct & Test Methods	Endpoints	Acceptance Criteria
A	Navii shows better or no worse results in Ramp, Stairs and Level Ground activities compared to prescribed prosthesis	Specific questions (see Annex 8.8)	Rating: Same, better, worse	Overall results for Navii are same or better than for Rheo Knee, with no more than 20% rating it worse, overall for all questions.
B	Navii shows a good level of overall satisfaction in activities of daily living	Subset of PEQ (see Annex 8.4) Specific Questions (see Annex 8.8)	PEQ Rating	Comparison Subset PEQ pre vs post. Navii not worse than prescribed.
C	Mobility is no worse with Navii compared to prescribed MPK	2 MWT	Distance walked in 2MWT (meters)	No significant reduction in distance walked on 2MWT with prescribed knee/Navii
D	Balance during ambulation is no worse with Navii compared to prescribed MPK	TUG	Time to complete TUG (seconds)	No significant increase in time needed to complete TUG with prescribed knee/Navii
E	Mobility is no worse with Navii compared to prescribed MPK	PlusM	PlusM Score	No significant reduction in PlusM Score with prescribed knee/Navii
F	Gather experiences on perceived safety and balance with Navii compared to prescribed knee.	ABC	ABC Score (0-100%)	Acceptable patient-reported perceived safety and performance

7.1 Additional Outcome measures:

8 Design of the Clinical Investigation

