8.1 General

The test will be a non-randomized single group repeated measures open label prospective design with observational and self-report measures.

Amputees are a small proportion of the general population. The population group specified in the inclusion/exclusion criteria is a further subsample of amputees. For practical reasons, i.e. to achieve statistical power, it is therefore more feasible to use within-subject comparison rather than creating study arms to compare. Furthermore, as mobile amputees generally have and use a prosthetic device for their daily activities, within-comparison is feasible comparing to the subject's previous device.

All investigational activities will be conducted at the Össur Orlando site.

As stated above the primary endpoint is Satisfaction on descending stairs, see Table 5, and the secondary endpoints are satisfaction on descending ramps, balance confidence and standing comfort in that respective order of significance. In addition, there are two exploratory endpoints on mobility and balance during ambulation. See previous chapter on objectives and hypothesis and Table 5 for rationale.

Drop-outs and withdrawals will not be replaced.

Instruments for data collection will include the following:

The Prosthesis Evaluation Questionnaire (PEQ) measures prosthetic-related quality of life. It consists of 82 items grouped into nine subscales. In addition, there are individual questions not contained in the subscales regarding satisfaction, pain, transfers, prosthetic care, self-efficacy, and importance¹⁸. This study will include a set of subscales from the PEQ, including specific questions on descending activities.

TUG The Timed Up and Go (TUG) is a tool used to test basic mobility skills by asking the subject to stand up from a chair (which should not be leaned up against a wall), walk a distance of 3 meters, turn around, walk back to the chair and sit down

2MWT is a measurement of endurance that assesses walking distance over two minutes.

ABC is a Patient-reported outcome measure that asks individuals to rate how confident they are that they will not lose their balance while performing 16 different activities.

PLUS-M (Prosthetic Limb Users Survey of Mobility) is a self-report instrument for measuring mobility of adults with lower limb amputation.

Specific questionnaire: In-house generated questionnaire on specific features in the investigational device.

Log file: User should log device use and events.

Video

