8.6 Responsibilities

Principal Investigator (PI) / Local Principal Investigator (LPI)

- Screen subjects
- Explain trial to participants
- Responsible for obtaining informed consent from test subjects
- Conduct trial procedures
- Fit users with trial device and provide training and back to their current prosthesis
- Investigate possible vigilance cases/SAEs
- Technical support

Co-Investigators (CI)

- Explain trial to participants
- Obtaining informed consent from test subjects
- Conduct trial procedures
- Fit users with trial device and provide training and back to their current prosthesis
- Collect Data
- Technical support

Monitor

- Train site staff on study procedures
- Monitor trial
- Analyze results
- Write report

Sponsor Research assistants (SRA)

- Technical support
- Support in data collection

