h) In case of EDS, database entry is locked after final patient data is entered. Database is closed and de-identified data exported by the sponsor Co-investigator/Monitor on completion of close-out monitoring activities including resolution of all data queries. Smart Trial audit history is extracted for records of monitoring activities. Exported de-identified data is stored on password protected PC intranet for analysis. In case of paper based data collection, de-identified data is scanned and shared with the sponsor Co-investigator/Monitor after data collection is complete.

Representatives of the sponsor, sponsor co-investigators and monitors, will be present at the study sites. A declaration of confidentiality to be signed by the representatives, ensures necessary data protection. Sponsor representatives will only observe and not interact with subject during the investigational procedures.

i) The data retention period for unlinked clinical data will be a minimum of 5 years in accordance with ISO 14155:2020. Clinical investigation documents, including but not limited to CIP, CIB, CRFs and clinical investigation report(s) should be incorporated into the device technical documentation under the quality management system of the manufacturer.

k) A Clinical Investigation Report (CIR) will be generated by Össur Medical Office. The report will be stored with the device technical file within Össur Quality Management System, along with the unlinked data and all accompanying investigational documents, according to the R&D and Quality documentation procedures. Subjects participating in the study can have access to the results, on demand, when the CIR is internally published.

Study results, data, and documentation will be stored for a minimum of 5 years.

14 Evaluation of Adverse Events and Device Deficiencies

For a list of foreseeable adverse events and anticipated adverse device effects, together with their likely incidence, mitigation or treatment see chapter 13.2 above and 7 in the Clinical Investigator's Brochure [2].

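### The plan does not say whether the visit 1 interview feeds criterion A, and at neither visit does it keep the same/better/worse ratings private from the staff who fit and train the subject.

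*Combined protocol and SAP*

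**What the plan says.** **Criterion A.** Row A of Table 5 (section 7) uses "Specific questions (see Annex 8.8"), rated same, better or worse. It passes if at most 20% rate Navii worse, taken over all questions together. Section 8.1 describes the instrument as an "In-house generated questionnaire on specific features in the investigational device".

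**Visit 1.** The synopsis and section 8.4 ii describe what follows the tasks on Navii. They call the question set standardized and say that the subject's "satisfaction will be asked as a semi-structured interview, and the responses are documented". No interviewer is named. At the same step Table 7 reads "Subject fills in set of questionnaires (Specific questions, comparison").

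**Visit 2.** Section 8.4 ii has subjects complete the same questionnaires as at visit 1. Section 8.4 iii says that the "device and performance specific questionnaires, will be used and filled in at two separate points in time". Table 7 repeats the row for the specific questions and lists ad hoc feedback before it.

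**Who is there.** Section 8.6 has both the PI/LPI and the co-investigators conduct trial procedures, and gives both this duty: "Fit users with trial device and provide training and back to their current prosthesis". Co-investigators also collect data. Section 8.1 adds: "All investigational activities will be conducted at the Össur Orlando site". The trial is open label (8.1) and subjects are not blinded (section 9). The only limit on contact is in 13.9: "Sponsor representatives will only observe and not interact with subject during the investigational procedures".

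**The concern.** A same/better/worse answer is a direct judgement on the product. The subject knows which knee is which and is at the manufacturer's site. The people running the session are those who fitted the knee and taught its use. A subject who speaks the answer to them, writes it in their view, or has just talked the device over with them, may be reluctant to say worse.

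Criterion A counts worse answers and has the only numeric pass limit in the readable Table 5. Each worse answer that becomes same or better lowers the counted quantity, so the error runs one way, towards a pass. Section 10.1 assesses the primary hypothesis descriptively and assigns methods separately to B–E and to F, which leaves A as primary by elimination (although 8.1 names satisfaction on descending stairs as the primary endpoint). Section 8.4 iii credits only the PEQ subset as a valid instrument. How the in-house rating is administered is therefore one of its few safeguards.

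**Working it through.** The plan has no figure to reproduce: 10.2 gives a convenience sample with no error rate, power or effect size. The check is mainly a reading of the text.

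**1. Mode of administration, side by side**

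- Visit 1, synopsis and 8.4 ii: standardized questions asked as a semi-structured interview, answers documented.
- Visit 1, Table 7, same step: specific questions and comparison filled in by the subject.
- Visit 2, 8.4 ii and Table 7: questionnaires completed or filled in by the subject. No interview is described, but ad hoc feedback is listed before the form.
- Both visits, 8.4 iii: device-specific questionnaires filled in.

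The interview and the form share a place in the visit 1 sequence and a subject (device performance and satisfaction). They may be one instrument described in two ways, or two instruments. Annex 8.8 could settle this but is blacked out, which is not a fault in the plan. No readable passage says which visit 1 answers, if any, count for criterion A. Section 7 sets the Navii measurement at the 4-week visit.

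**2. Privacy of the answer**

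The no-interaction rule in 13.9 covers sponsor representatives only. The PI/LPI and co-investigators fit, train and run procedures (8.6). No readable passage requires the rating to be given out of their view or before discussion with them.

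**3. Direction and possible size**

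Let p be the true share of worse judgements and s the share of those softened to same or better. The expected recorded share is p(1 − s), which is below p for any s > 0. This holds whether answers are pooled or not. Neither p nor s is in the documents, so the values below are assumptions.

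- With p = 30%: s = 10% gives 0.30 × 0.90 = 27%; s = 25% gives 0.30 × 0.75 = 22.5%; s = 50% gives 0.30 × 0.50 = 15%.
- Softening needed to bring the expected share down to the limit is s = 1 − 0.20/p. For p = 30% this is 1 − 0.20/0.30 = 33%; for p = 40% it is 1 − 0.20/0.40 = 50%.

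If, contrary to the pooled wording, each subject gave one overall rating, the limit at n = 10 (minimum completers, 8.3) is 0.20 × 10 = 2. At n = 13 (maximum, 10.2) it is 0.20 × 13 = 2.6, so also 2. The chance of passing is then the binomial P(X ≤ 2) with probability p(1 − s):

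| p | s | n = 10 | n = 13 |
|---|---|---|---|
| 30% | 0 | 0.383 | 0.202 |
| 30% | 10% | 0.466 | 0.275 |
| 30% | 25% | 0.602 | 0.413 |
| 30% | 50% | 0.820 | 0.692 |
| 40% | 0 | 0.167 | 0.058 |
| 40% | 25% | 0.383 | 0.202 |
| 40% | 50% | 0.678 | 0.502 |

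Under pooling a single answer counts for much less. With an assumed 10 questions, 13 subjects give 130 answers and a limit of 0.20 × 130 = 26, so one answer moves the rate by 1/130 = 0.8 percentage points. The table illustrates sensitivity and does not estimate the bias in this trial. It also treats s = 0 as the comparison, which assumes a private form removes all softening.

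**The case against.** The strongest reply is that there may be no contradiction. Wherever the device-specific instrument is named, it is a questionnaire or is filled in. The synopsis calls what precedes the testing of descent modes a first feedback round, which fits an interview separate from the form. The questions are also described as standardized, which limits how far their wording can drift. All of this stands, and it is why the point is that the plan leaves the link open, not that it puts criterion A in an interview.

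Several stronger readings are tempting but unsupported:

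- *The deciding rating is spoken to the fitter.* The interview is described only at visit 1 and names no interviewer. The 4-week form is described as filled in.
- *One softened answer turns a fail into a pass.* At 13 subjects, 3/13 = 23.1% fails and 2/13 = 15.4% passes, but only with one rating per subject. Table 5 pools all questions.
- *Subjects' ratings are a mixture of two modes.* Nothing says that different subjects are handled differently.
- *Sections 8.6 and 13.9 conflict over sponsor research assistants.* Supporting data collection need not mean dealing with the subject; video and device logging are also planned.

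It is also fair to say that self-completion does not remove open-label bias. What survives is that no text says whether the interview counts, and none shields the rating from the fitting staff or from prior discussion at either visit.

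**Conclusion.** The point holds as a gap in the wording that a cheap change closes. It does not show that criterion A is invalid. The plan does not say whether the visit 1 interview feeds criterion A. At visit 2 it lists ad hoc feedback before the form, and at neither visit does it keep the answers from the people who fitted and trained the subject. Any resulting bias would favour a pass.

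Its size cannot be computed from the documents: the number of questions is not readable, no softening rate is given, and the criterion pools all questions. The conclusion rests on two readings. One is that the order of rows in Table 7 reflects the order of the visit. The other is that the staff listed in 8.6 as fitting and training are those present when the form is completed, which the documents allow but do not state.

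**What to change.** State in 8.4 and Table 7 that:

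1. At both visits the subject self-completes the Annex 8.8 same/better/worse ratings, in Smart-Trial or on paper, before any interview or ad hoc feedback. In Table 7 the visit 2 ad hoc feedback row moves to after the form.
2. Fitting staff and sponsor representatives do not view the answers while they are being given. Later review of case report forms for completeness (13.9) is unaffected, and the LPI can still be present at the visit as 13.3 requires.
3. Only the self-completed answers at the 4-week visit count for criterion A.
4. The semi-structured interview is kept for free-text feedback.

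If the sponsor already intends two separate instruments, items 3 and 4 simply record that.

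The cost is protocol wording. Tablets and paper forms are already in the equipment list in 8.1, and sample size and number of visits do not change. The small downside is that staff cannot clarify a question while the rating is being given.

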8.5 Compensation

Subject

8.6 Responsibilities

Principal Investigator (PI) / Local Principal Investigator (LPI)

- Screen subjects
- Explain trial to participants
- Responsible for obtaining informed consent from test subjects
- Conduct trial procedures
- Fit users with trial device and provide training and back to their current prosthesis
- Investigate possible vigilance cases/SAEs
- Technical support

Co-Investigators (CI)

- Explain trial to participants
- Obtaining informed consent from test subjects
- Conduct trial procedures
- Fit users with trial device and provide training and back to their current prosthesis
- Collect Data
- Technical support

Monitor

- Train site staff on study procedures
- Monitor trial
- Analyze results
- Write report

Sponsor Research assistants (SRA)

- Technical support
- Support in data collection

8.7 Study monitoring and Oversight

The study monitor(s) will monitor the study to ensure all procedures are followed correctly and according to the study protocol. The study monitor will gather and review all study data and inform the PI of missing data or nonconformities to the study protocol.

The study monitor(s) and **PI** will maintain communication on a minimum biweekly basis, via telephone and email. The **PI** will provide the study monitor(s) with information of all scheduled study visits. The study monitor will visit each investigational site at least once while a study visit takes place.

9 Investigational Device Accountability

The investigational device will be provided as needed for the study population. Devices will not be packaged but will be labeled according to **FDA** regulatory requirements. Subjects will not be blinded.

The **PI** will keep records documenting the receipt, use and return of the investigational device in the Investigational Device Management Form, including:

- Date of receipt
- ID of each investigational device
- Step count at start and end of investigation
- Period of use
- Subject ID
- Date of device return
- Date of return of unused, expired or malfunctioning investigational devices, as applicable

10 Statistical Considerations

10.1 Statistical design and procedures

The primary hypothesis will be assessed with descriptive statistics only, comparing the rates prior-evaluation (current device) and post-evaluation (investigational device). For hypotheses B, C, D, E will be assessed with mixed models effects where MPK type is used as fixed effect, subgroup analysis, and subject as random effect. F will be assessed with exploratory methods. All data will be analyzed exploratively for subgroup effects for input into further studies but not used to support claims.

Acceptance criteria for the data, as applicable, is defined in Table 4 **Endpoints, test methods and hypotheses**. Subgroup analysis will not be performed as no subgroups are defined.

